#### **4) OBJECTIVE(S)/SPECIFIC AIMS AND HYPOTHESES**

We conducted an extensive review of the published literature and currently funded NIH studies but found surprisingly limited research on development of a CCM model to treat ED/AUD in PCMHs. Thus, to the best of our knowledge, this would be among the first studies in this area. In addition, while the general assumption is that early intervention in primary care can be effective, there is very limited knowledge about whether patients will engage in more than a brief intervention or how best to accommodate important aspects of patient-centered care such as patient preferences. Finally, little is known about non- response to ED/AUD treatment in primary care and what stepped care approaches can feasibly be implemented in PCMHs using a team-care approach.

The primary aim of this proposal is to develop and test a chronic care model (CCM) to treat excessive drinking and Alcohol Use Disorders (ED/AUD) in a patient centered medical home (PCMH) setting using the stage model of intervention development. The study proposes to adapt the collaborative care model (CC) for treating depression in primary care to use with ED/AUD and then test the adapted model for feasibility, acceptability, and clinical utility. If evidence supports the model, the long-term aim of the study is to develop the necessary protocols, site preparation, and design specifications to proceed to submitting an RO1 application.

The study will be conducted in two phases using a mixed methods approach. Phase I (5 months) will involve initial adaptation of the CC model for depression to ED/AUD (referred to hereafter as CC-AUD). During this phase, relevant CC for depression protocols, measures, and procedures will be adapted for ED/AUD and piloted test on 15-20 participants recruited in a PCMH. Phase II (6 months) will involve model refinement based on iterative cycles of patient and PCMH staff feedback. During this phase, participants (n=60) will be recruited, assessed, and followed for three months. Iterative development will focus on two themes: 1) maximizing patient engagement while balancing this feature with 2) the resource and expertise constraints of treating ED/AUD in a PCMH. Study results will be analyzed and lessons learned will be used to develop a refined model. a small randomized controlled trial (RCT) of the model..

Aim I. Adapt the CC model for depression to treat ED/AUD and implement the model (CC-AUD) in a PCMH.

Aims II. Use iterative, recursive, and bidirectional features of the stage model to refine CC-AUD using a mixed methods approach.

Specific hypotheses are not provided for Phases I and II of the study as we are exploring and refining possible model options. For Phase III of the study, which is the randomized controlled trial and will be submitted as a separate IRB protocol, will provide specific hypotheses on what we expect to see from the models.

## **5) RESOURCES AVAILABLE TO CONDUCT THE HUMAN RESEARCH**

Subjects will be recruited as part of normal SBIRT procedures already being conducted at the [name] General Internal Medicine site in Great Neck, NY. Normal SBIRT procedures include the pre-screening of all scheduled patients by medical assistants to identify initial substance use risks, and then further assessment to identify risk classification of the patient based on their substance use patterns and counseling by an SBIRT Health Coach for patients as needed based on this assessment. Patients identified as excessive drinkers during the standard SBIRT procedures will be asked by the SBIRT Health Coaches (HCs) about their interest in a study on treatment for problematic alcohol use in the primary care setting. As all clinic patients are being routinely screened for alcohol, we will have a large pool of patients screened from which to identify excessive drinkers. Based on SBIRT data collected, we estimate that 75% of the patients or about 33 per month have a primary alcohol problem and would not be excluded for other reasons. We estimate that about 2/3 of eligible participants would be classified as at-risk drinkers with the remainder in the other categories (i.e., Problem Drinkers, Alcohol Use Disorder with Physiological Withdrawal, and Alcohol Use Disorder with Chronic or Complex Presentation). Thus, assuming that 50% consent to participate, we estimate n=24 participants per month would be available to enroll in the study and about eight of these would meet problem drinking criteria. We note that of the 526 participants screening positive and offered a brief intervention at the [name] site, only 3 refused. Thus, we anticipate a positive response from participants and consider our recruitment projections as conservative estimates.

## **6) RECRUITMENT METHODS**

Participants will be recruited via the SBIRT program at the [name] General Internal Medicine Clinic. In addition, patients of other Northwell Health Department of General Internal Medicine (DGIM) sites may be referred to the [name] practice to participate in this study. All patients receive SBIRT screening, conducted by the Health Coaches (HCs). During the screening, HCs will identify potential participants for this study based on study eligibility criteria. For individuals who screen positive and meet study criteria, the HC will offer the opportunity to participate in the study and conduct further assessment if the individual is interested. In cases where individuals are ambivalent about participation, they will be handed an informational card about the study with a way to contact study staff. This card will be submitted to the IRB for approval prior to distribution to patients.

## **7) ELIGIBILITY CRITERIA**

We expect to recruit a total of 85 participants for Phase I and II of this study based on the following inclusion/exclusion criteria:

**Inclusion Criteria:** Participants must: 1) receive care at the [name] General Internal Medicine clinic and/or other Northwell Health DGIM sites; 2) have an estimated weekly consumption of greater than 14 drinks for men and 7 drinks for women or experience

at least one binge drinking day (i.e., 5 or more drinks for men and 4 or more drinks for women) per week; 3) demonstrate observable fluency in English language; 4) have no recognizable cognitive impairment.

**Exclusion Criteria:** Participants will be excluded from the study if they: 1) report substance use other than cannabis, nicotine, or caffeine in the last year; 2) report using cannabis “daily or almost daily” and that this use is problematic and the primary concern compared to their alcohol use, as indicated in the SBIRT screening; 3) present with a serious psychiatric illness or substantial suicide or violence risk, as assessed via a chart review, reported by the primary care treatment team (e.g., the Primary Care Physician [PCP]), and/or reported by the potential participant in the initial screen; 4) are on probation or parole as reported in the initial screen; 4) have an organic mood/mental disorder; 5) is pregnant, breastfeeding, or trying to become pregnant as reported in the initial screen; 6) report being enrolled in current substance use treatment in the initial screen.

## **8) NUMBER OF SUBJECTS**

In the [name] primary care setting from where participants will be recruited and seen, approximately 526 patients are pre-screened per week for alcohol use problems. Of these patients, approximately eight receive alcohol use brief interventions. It is estimated that all 526 patients will be pre-screened for our study and the eight who receive brief interventions will be offered to participate, if they meet initial eligibility criteria. We expect that 50% of these patients or 4 individuals per week will be consented into our study. Other DGIM sites from where staff can refer patients to the study, the number of pre-screens for alcohol use problems are comparable. As a result, we expect to enroll a total of 85 participants, which includes 25 for Phase I of the trial and 60 for Phase II.

## **9) STUDY TIMELINES**

Enrollment for the proposed study is expected to last for approximately one year. Each participant will be in the study for 12 weeks. We expect to complete this study (Phases I and II) in Fall 2017.

## **10) ENDPOINTS**

Over the 12 weeks of the study, there will be five assessment points at weeks 0, 1, 4, 8, and 12, which all participants will receive. Participant response and safety will be assessed at each assessment point. In addition, participants will be monitored daily via Ecological Momentary Assessment data (EMA) comprising a brief questionnaire about their drinking. The HC will monitor participants' adherence to these surveys and their study visits and make outreach as needed. Notably, participant response to treatment will be assessed at week 4 and a stepped-care approach will be applied in the case that the participant has not responded to the initial treatment that he or she chose. For instance, participants who chose to receive a behavioral intervention will be offered medication (i.e., naltrexone) if they have not shown progress in their treatment as evident by a significant reduction in drinking.

Some participants will also attend treatment appointments in the 12 weeks of this study, some of which will overlap with the assessment appointments. Participants will have biweekly medication management appointments and/or potentially 4 to 12 sessions of behavioral treatment.

## **11) RESEARCH PROCEDURES**

During Phase I (Initial Model Implementation), we will prepare all relevant new materials, adapt existing treatment and assessment protocols, fine-tune all new procedures, and train the primary care treatment team (including HCs, Medical Doctors [MDs], Nurse Practitioners [NPs], Registered Nurses [RNs], and Behavioral Health Specialists [BHSs]) on the new intervention protocols. Because all staff are currently either working as part of SBIRT or in other roles in Psychiatry and Medicine, we anticipate a rapid start-up. In addition, the BHSs are already trained in the delivery of the proposed interventions.

During Phase II (Iteration and Model Refinement), we will iterate and refine the model that was tested in Phase I. We will focus on key issues of patient engagement, balancing treating patients within the PCMH versus need to refer complex cases to specialty care as well as issues related to staff burden, workflow and resources. We will focus on examining the utility of medical record screening, refining the content and methods to deliver personalized feedback on alcohol consumption and health and assessing their impact of increasing patient motivation as well as PCP receptivity to including alcohol interventions as part of PCMH care. We will pay special attention to tracking non-adherence, and adjusting interventions for non-responders. We will also carefully examine workflow and resources required to manage patients. For example, how much time is required from specialist consultants and what types of consultation (e.g., caseload supervision, patient consults) are most informative. We will use these data to generate an estimate of staff resources required to treat eligible participants.

Below we describe the procedures to be conducted at each endpoint in both phases of the study, in addition to specific procedures related to our stepped-care approach and risk/safety monitoring.

**Week 0: Pre-enrollment:** Participants will be recruited through the Screening, Brief Intervention, and Referral to Treatment (SBIRT) program that is already a standard practice in the primary care site, where they are patients or to which they are referred to from other Northwell DGIM sites. As part of SBIRT standard practice in this setting, all patients are systematically screened for risky alcohol use by a medical assistant and a health coach, using the Alcohol Use Disorders Identification Test (AUDIT), a self-report validated screening tool. In addition, for patients who screen positive for risky alcohol use, the HC provides a brief intervention, which includes feedback about their drinking, a discussion about motivation to reduce use, and planning around reducing or stopping alcohol use. During this interaction, HCs will assess if patients are eligible for the study based on the criteria. The HC will provide a brief explanation of the study to patients who appear initially eligible to participate. Further eligibility screening will be provided either that day or another day when the patient is available, if he or she expresses interest in participating.

**Week 0: Eligibility Screening:** Participants will be recruited for this study based on our inclusion/exclusion criteria described above. Those participants who are interested in the study will be initially consented (General Consent) by the HC and will complete further measures (i.e., the Timeline Follow Back [TLFB] for the past 60 days and the Composite International Diagnostic Interview-Alcohol Module [CIDI-Alcohol]), assessing for drinking criteria and establishing risk classification for treatment options. Other inclusion/exclusion criteria (i.e., drug use, mental/organic disorders, suicide/violence risk, legal involvement, and pregnancy) will be evaluated at this point via self-report, chart review, and/or in consultation with the primary care clinical team (e.g., the primary care physician). Patients who endorse withdrawal criteria on the

CIDI-Alcohol (i.e., endorse experiencing at least two withdrawal symptoms in the last year after not drinking for a few hours or days, if any of those symptoms include hallucinations or seizures, or if they report drinking to reduce withdrawal symptoms in the last year) will also meet with a Registered Nurse (RN; supervised by an MD), Nurse Practitioner (NP), or a Medical Doctor (MD) to assess active withdrawal symptoms and appropriateness of outpatient detoxification treatment. In such cases, the RN/NP/MD will complete the Clinical Institute Withdrawal of Alcohol Scale, Revised (CIWA-Ar) and assess for medical (e.g., brittle diabetes, unstable heart failure, advanced liver disease) and compliance (e.g., no family support at home to assist) issues with which outpatient detoxification would be contraindicated. Those participants who do not have medical or social contraindications and score below 15 on the CIWA-Ar will be offered outpatient detoxification as part of standard care at the [name] Internal Medicine Clinic. These participants will be grouped in the AD-W group and offered treatment as per the description below. Participants' insurance will cover the cost of the detoxification treatment. Participants who score above 15 on the CIWA-Ar or experience medical and/or social contraindications for outpatient detoxification will be referred for inpatient detoxification or other warranted treatment and classified into the AD-CMPLX group, as described below.

Eligible participants will be classified (i.e., random assignment will not be used) into one of four groups by the HC after the above assessment is completed:

*At-Risk Drinkers (AR)*. AR will include individuals who exceed NIAAA guidelines for weekly consumption (>14 standard drinks [SD] for men or 7 drinks for women), those who exceed NIAAA daily limits (>5 SD for men or >4 SD for women), or those whose medical conditions contraindicate any alcohol consumption. AR will be followed up at week 4, 8, and 12 assessments and will not be offered additional treatment after the brief advice they receive as part of SBIRT.

*Problem Drinkers (PD)*. PD will be defined based on weekly consumption (> or = 24 SD for men or > or = 14 SD for women) or a pattern of regular binge drinking (>3 times per month). PD will be offered a choice of either four sessions of Motivational Enhancement Therapy (MET) or 12 weeks of daily naltrexone with medication management.

*Alcohol Use Disorder with Physiological Withdrawal Drinkers (AD-W)*: Participants meeting criteria for DSM-5 Alcohol Use Disorder with physiological withdrawal will receive outpatient detoxification as part of standard care, unless medically or socially contraindicated (described above). Upon completion of outpatient detoxification, participants will be offered 12 weeks of daily naltrexone plus medication management or 12, weekly sessions of **M o d i f i e d B e h a v i o r a l S e l f - C o n t r o l T h e r a p y ( M B S C T )**.

*Alcohol Use Disorder with Chronic or Complex Presentation Drinkers (AD-CMPLX)*: Participants in this group will include those who meet criteria for DSM-5 Alcohol Use Disorder, report inpatient treatment for alcohol use and/or other mental health issues within the last five years, experience social problems (i.e., unstable housing) that would suggest the need for more intensive psychosocial treatment, or are deemed not appropriate for outpatient detoxification treatment and in need higher-level of care as assessed by the NP/MD performing the CIWA-Ar assessment. Participants classified at AD-CMPLX will be referred to specialty substance use treatment based on the SBIRT protocol, where participants are referred to an outpatient treatment program that best fits their needs. In the case that these participants refuse a referral to specialty care, a second attempt will be made to do so at week 1. In the case that the second attempt is not successful, they will be offered MBSCT, abstinence-based treatment, focused on connecting them with specialty care, as part of the study.

Once participants are grouped and offered treatment options for their risk classification, they will choose a preferred treatment course and be scheduled for their next appointment with an RN/NP/MD to administer naltrexone or a Behavioral Health Specialist (BHS) to conduct the behavioral interventions. Each respective clinician will complete either the Medication Intervention Consent or the Behavioral Intervention Consent with the participant at their next appointment. Notably, participants are free to change their treatment choice during the consent process (described below) with the clinician. If they do so, they will be scheduled for another appointment with the appropriate clinician. All participants will be informed that they are being asked not to pursue any other formal substance use treatment until after the week 12 assessment of the study, unless they are in the AD-CMPLX group and referred to treatment as part of this study. If they decide to pursue alternative treatment, study staff will facilitate referrals. The participant will continue to be followed in the study via follow up assessments in order to learn about the progress of the participant which is valuable in our effort to test a feasible treatment model.

**Weeks 1-12:** During this period, participants in the PD and AD-W groups will receive treatment (see procedure as follows) and assessments, while the AR and AD-CMPLX groups will be followed in assessments only. All groups will be assessed for appropriateness of stepped-care at week 4.

Participants, who choose the medication intervention, will attend medication management in-person at the primary care clinic. Appointments would be conducted by a NP, an MD, or an RN, who is supervised by an MD,. These appointments will occur weeks 1, 2, 4, 6, 8, 10, and 12. At their week 1 appointment after consent has been signed, the medical professional will assess the participant for appropriateness to take medications. They will conduct a medical exam, review the participant's chart, and may consult with his/her primary care clinical team.

Participants who choose behavioral interventions will have appointments conducted at the primary care clinic or via televideo, based on the preference of the participant. Behavioral Health Specialists (BHSs), who are licensed therapists or therapists supervised by licensed clinicians, will conduct the treatment. Participants receiving MET will have four sessions at weeks 1, 2, 4, and 8. Participants receiving MBSCT will receive weekly sessions from week 1 to 12.

In addition to regular treatment appointments, follow up assessment appointments will occur with the HC at weeks 4, 8, and 12. Each assessment appointment will occur after the treatment session scheduled for that day. These appointments can occur in-person or via televideo based on each participant's preference and will be conducted by the HC. At each appointment, the participant will complete the Timeline Follow Back (TLFB), a treatment addendum, and patient satisfaction measures. Participants will be monitored for risk and safety at each of these appointments as described below.

Furthermore, at week 1, participants will meet with a HC to complete a demographics questionnaire and receive training and instruction on the Ecological Momentary Assessment (EMA; described below). Because participants will be using smartphones, we will show them how to use their phones in a way that increases the security and confidentiality of the online surveys and the texts they receive. Based on our experience in previous studies, participants complete about 80% of the required surveys, which is significantly higher than expected. Note that EMA data is in electronic format and available in real-time to the HC. We will monitor EMA diary completion continuously to increase compliance and will have the required data available

for safety monitoring. Participants will have the option to participate in the study even if they do not have a smartphone or refuse to use it to complete EMA. In such cases, participants will not complete EMA.

At week 4, participants will be assessed for response to the treatment intervention that they chose and offered an alternative treatment via the stepped care procedure below in the case that they do not respond. Response will be defined as drinking below study drinking inclusion criteria and demonstrating adequate progress in treatment without adverse response (based on clinician's assessment of participants' drinking, attendance, engagement, and effort and/or possible side effects if receiving naltrexone). A participant will be deemed a non-responder if his or her drinking exceeds NIAAA guidelines for weekly ( $>14$  SD for men or 7 drinks for women) or daily ( $>5$  SD for men or  $>4$  SD for women) limits.

**Stepped Care:** Participants will be offered stepped care if they are deemed to be a treatment non-responder at their week 4 appointment. During their treatment visit at week 4, they will be assessed by the HC and their clinician for treatment response based on the criteria described above. The HC will assess participants' drinking based on NIAAA guidelines and the clinician will assess participants' progress in treatment. If a participant is deemed a non-responder, the clinician will discuss alternative treatment options with him or her. Stepped care options will be offered to the AR, PD, and AD-W risk classification groups at their week 4 assessments in the following way:

For the AR group, participants who are deemed non-responders will be offered an additional session of Brief Advice similar to what they received as part of the SBIRT protocol. This additional session will occur at the same time as their assessment appointment at week 4.

For the PD and AD-W groups, participants, who chose a behavioral intervention, will be offered naltrexone and medication management. These participants will be scheduled for an appointment with the respective clinician, preferably in the same week, in order to undergo consent, to evaluate medication appropriateness, and, if appropriate, to commence with the alternative treatment. Participants, who chose naltrexone and medication management, will be offered either a behavioral intervention (i.e., MBSCT) in addition to naltrexone or topiramate as an alternative medication for reducing drinking. This medication will be started on the same day, while the behavioral intervention would be scheduled for a different appointment with a BHS, where an additional consent would be completed. Participants will have the option to deny alternative treatment if they believe it is still the appropriate course of action during these phases of the study as long as it appears safe for them to continue (e.g., no adverse side effects to the medication are noted). The goal is to learn about the effectiveness of these different treatment models in these phases of the study through an ecological application of the models in a clinical setting, where patients would otherwise be free to deny an alternative treatment.

**Risk/Safety Monitoring:** Participants of this study will be patients who are receiving care at the [name] Internal Medicine Clinic or another Northwell Health DGIM site. Therefore, their health is actively monitored by the Primary Care Physician (PCP) at the clinic, who will be notified of the participant's participation throughout the study. In addition to this monitoring, the clinicians meeting with the participants for treatment will assess their well-being at each assessment (at weeks 4, 8, and 12) along with the HC drinking assessments and the daily EMA data monitoring. At the week 4, 8, and 12 assessments, the clinicians will

perform a risk and safety assessment. Significant deterioration of note is defined as a significant increase in drinking since the baseline interview (more than 25%); a significant increase in depression, anxiety, or other mental health symptoms; instability in life circumstances that would suggest a need for immediate treatment; or suicidal or homicidal ideation. If any of these indicators are present, as a first-line of treatment, participants will be referred to the clinical team at the primary care clinic for additional treatment or evaluations. If a higher level of care is warranted, participants will be referred to appropriate care, such as intensive outpatient treatment, inpatient detoxification, or outpatient psychiatric treatment, and continued to be monitored at their assessment visits. For participants who present an imminent risk of harm to self or others, or an inability to care for themselves, the primary care clinical team will evaluate the patient to determine the need to activate EMS, who will then take the patient to the emergency room to be evaluated for possible inpatient psychiatric admission.

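### Participants judged unsuitable for outpatient detoxification who refuse referral twice are offered abstinence-based therapy with no repeat withdrawal review

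*Combined protocol and SAP*

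**What the plan says.** The relevant text is mainly in section 11 (Research Procedures) of the combined protocol and SAP.

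- **Week 0: Eligibility Screening.** Patients go to an RN, NP or MD if they "endorse experiencing at least two withdrawal symptoms in the last year after not drinking for a few hours or days", if they report hallucinations or seizures, or if they drink to relieve withdrawal. The clinician completes a CIWA-Ar and looks for medical and social contraindications to outpatient detoxification. Those who score above 15 or have a contraindication "will be referred for inpatient detoxification or other warranted treatment and classified into the AD-CMPLX group".
- **AD-CMPLX paragraph.** The group has several entry routes, including past inpatient treatment, social problems such as unstable housing, and unsuitability for outpatient detoxification. All are referred to specialty treatment. If they refuse, "a second attempt will be made to do so at week 1". If that fails too, "they will be offered MBSCT, abstinence-based treatment, focused on connecting them with specialty care, as part of the study".
- **AD-W paragraph.** For those suitable for outpatient detoxification: "Upon completion of outpatient detoxification, participants will be offered 12 weeks of daily naltrexone plus medication management", or weekly MBSCT as the alternative.
- **Weeks 1-12.** PD and AD-W receive treatment, "while the AR and AD-CMPLX groups will be followed in assessments only".
- **Section 19 (Research Related Harm/Injury).** Round-the-clock access to an on-call physician is stated for participants who receive outpatient detoxification.

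**The concern.** The refusal rule does not distinguish how a person came to be AD-CMPLX. Someone there because of unstable housing and someone there because a clinician found outpatient detoxification unsafe follow the same steps, and both can end in abstinence-based therapy. For the second person, stopping drinking is the event that carries the withdrawal risk identified at week 0, and the managed route has just been declined twice. At that point the plan requires no medical response.

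What is at stake is participant safety: a person who adopts the abstinence goal could stop drinking without supervision. The protocol's own screening item places withdrawal symptoms within hours or days of not drinking.

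**Working it through.** The plan states no figure to reproduce. The check is a trace of two pathways, followed by a look at each safeguard.

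**The two pathways**

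| Step | AD-W | AD-CMPLX by the withdrawal route |
|---|---|---|
| Week 0 RN/NP/MD review with CIWA-Ar | Yes | Yes |
| Result of that review | Outpatient detoxification acceptable | Outpatient detoxification not acceptable |
| Managed withdrawal before MBSCT | Completed first | Declined, if referral is refused |
| Medical review after refusal | Not applicable | None stated |
| On-call physician access stated | Yes (section 19) | No |
| MBSCT may then be offered | Yes | Yes, labelled abstinence-based |

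The group judged at higher risk can reach the same therapy with fewer written protections.

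**Does any safeguard require a withdrawal check between the second refusal and abstinence work?**

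1. *Week 0 review.* It is withdrawal-specific, but it comes before the refusals and is what found the person unsuitable.
2. *Week 1 safety assessment (section 10).* Safety is assessed at every assessment point, week 1 included. No content is given for week 1. The listed week 1 tasks in sections 11 and 12 are consent, an enrollment note, demographics, survey training and, for those on medication only, a blood draw.
3. *Defined risk assessment (section 11, Risk/Safety Monitoring).* Here "the clinicians meeting with the participants for treatment will assess their well-being at each assessment (at weeks 4, 8, and 12"). For MBSCT the treating clinician is a behavioral health specialist (section 13).
4. *Deterioration triggers.* The drinking trigger is a rise of more than 25% from baseline. For baseline drinking b, complete cessation is (0 - b) / b = -100%, which cannot meet it. The other triggers are worsening mental health symptoms, unstable life circumstances that call for immediate treatment, and suicidal or homicidal ideation; an emergency route covers imminent risk or inability to care for oneself. These could pick up trouble once it appears. None names withdrawal or acts beforehand.
5. *Daily drinking survey.* A fall to zero would be visible to the health coach. The survey is optional, and no rule says such a fall should prompt a medical contact.
6. *Primary care oversight, section 17 monitoring and section 19 referral.* These run throughout and lead to inpatient detoxification for those who appear to need it. They too are reactive.

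**Interval.** From the week 1 referral attempt to the first risk assessment with defined content: (4 - 1) x 7 = 21 days. This is an upper bound on the time from the start of MBSCT, because the offer follows the failed attempt and a consent appointment comes next.

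**The case against.** The strongest reply is that the plan already contains a withdrawal-specific medical review, and that it is the reason these people are in AD-CMPLX. That is correct. A reader might infer that nobody medically assesses withdrawal before MBSCT. The week 0 CIWA-Ar rules that out; what is missing is a response after refusal.

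A reader might also infer that participants go unobserved until week 4. The documents do not support that either, given the week 1 safety assessment, weekly therapist contact, daily surveys for those who accept them, and primary care oversight.

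Nor does the plan tell these participants to stop drinking at once. MBSCT for this group is directed at linking them to specialty care, and its first stage is motivational (section 13), so a quit attempt may well not come early. This weakens the chain to harm. It does not remove it, because the therapy is still labelled abstinence-based and nothing holds that goal back until someone medical has agreed.

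Two further comparisons are tempting and should not be used. Medication patients have more scheduled medical visits, but an AD-W participant on MBSCT alone has none scheduled after detoxification either, so the contrast does not isolate AD-CMPLX. The week 4 stepped-care options omit AD-CMPLX, but that has no bearing on weeks 1 to 3.

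Finally, the clinic's SBIRT protocol and standard care, on which the plan relies, are not among the documents. They may say what happens when detoxification is refused, and clinicians may act sensibly without a rule.

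**Conclusion.** The concern holds in a limited form. The week 0 review is sound, but the refusal rule does not use its result. A person found unsuitable for outpatient detoxification who declines referral twice can be offered abstinence-based MBSCT with no repeat medical review, while the lower-risk AD-W group must complete detoxification first and has stated on-call cover. The general safeguards reduce the risk; none requires a withdrawal check before abstinence work begins.

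The number affected cannot be derived. Section 5 puts about two thirds of eligible patients in the at-risk group, leaving about 1 - 2/3 = 1/3 for the other three groups together. It gives no AD-CMPLX share and no refusal rate. The number is probably small.

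A reader might look for an effect on the drinking outcomes. There is none to claim: no endpoint or analysis changes. This is a participant-safety gap that should be closed.

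The conclusion rests on two assumptions: that refusing inpatient detoxification falls under the AD-CMPLX refusal rule, which is the only one stated, and that no clinic procedure outside these documents already supplies the missing step.

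**What to change.** In the AD-CMPLX paragraph of section 11, add a branch along these lines: participants judged unsuitable for outpatient detoxification who decline referral at both attempts have the week 0 withdrawal review, including the CIWA-Ar, repeated by an RN, NP or MD before MBSCT sets an abstinence goal. Until they are cleared, MBSCT serves only as engagement toward medically managed detoxification, and they are told not to stop drinking abruptly without medical supervision.

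Three matching edits follow:

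- In the Weeks 1-12 text, add an exception for AD-CMPLX participants who accept MBSCT under the refusal rule, since that text now says the group is followed by assessment alone.
- In the section 12 schedule, add a conditional CIWA-Ar entry after the second refusal.
- In section 19, extend the on-call physician access to these participants.

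The staff and the scale are already in the protocol. The first stage of MBSCT is motivational and its skills cover moderation as well as abstinence (section 13), so no new manual is needed. The cost is a few lines of text, one brief extra contact per affected participant, and a possible short delay to abstinence-goal sessions. Nobody is refused therapy, because MBSCT can go ahead as engagement in the meantime.
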